Potential participants will receive information in private clinic rooms for privacy. During all patient interactions, study team will do their best to ensure that no study materials/information will be left in view of others not associated with the project. The healthy volunteer arm will occur in a private laboratory.

Study outcomes during anesthesia for surgery. Follow up visits will be conducted in a private room in the clinic.
- 3 * Describe the availability of medical and/or psychological resources that subjects might need as a result of anticipated consequences of the human research:
There are always research staff available to the patient should the patient have any questions or concerns, and the Principal Investigator and/or Sub-Investigator's are likewise available to the patient.
- 4 * Describe the process to ensure that all persons assisting with the research are adequately informed about the protocol, the research procedures, and their duties and functions:
All study staff are required to go through a training process for the study with the principle investigator, which includes knowledge assessments and regular meetings to ensure that all staff are fluent in all aspects of the study.

ID: VIEW4DF83CB976400
Name: v2_Resources

Sites Where Research Activities Will Be Conducted

- 1 * Is this study a:
 Multi-Site
 Single Site
- 2 * Are you relying on an external IRB (not UM) to be the IRB of Record for this study?
 Yes No
- 3 * Are any other institutions/organizations relying on UM to be the IRB of Record for this study?
 Yes No
- 3.1 Attach the applicable regulatory documents here (i.e., IRB Authorization Agreement (IAA), FWA, local ethics approval, other IRB approvals, etc.). Final UM approval will be contingent upon final execution of all required regulatory approvals:
- | Name | Created | Modified Date |
|--|-------------------|-------------------|
| Midtown Campus IAA.pdf | 6/18/2015 4:24 PM | 6/18/2015 4:24 PM |
| University of Maryland Rehab and Ortho Institute IAA.pdf | 6/18/2015 4:23 PM | 6/18/2015 4:23 PM |
- 4 * Is UM the Coordinating Center for this study? (Applicable for multi-site studies. A Coordinating Center is responsible for overall data management, monitoring and communication among all sites, and general oversight of conduct of the project.)
 Yes No
- 5 Is VA the Coordinating Center for this study? (Applicable for Collaborative studies between the VA, UM and other sites. A Coordinating Center is responsible for overall data management, monitoring and communication among all sites, and general oversight of conduct of the project)
 Yes No
- 6 * Institution(s) where the research activities will be performed:
University of Maryland Medical System (Select below)
- * UMMS Sites:
UMMC Midtown Campus (formerly Maryland General Hospital)
University of Maryland Rehabilitation & Orthopaedic Institute (formerly Kernan Hospital)

ID: VIEW4DF870DF2C000
Name: v2_Sites Where Research Activities Will Be Conducted

Funding Information

- 1 * Indicate who is funding the study:
Department / Division / Internal
- 2 * What portion of the research is being funded? (Choose all that apply)
 Drug
 Other

- 3 Please discuss any additional information regarding funding below:
Funding will cover the different skin preps and the tools for obtaining culture.

ID: VIEW4DF85DF452400
Name: v2_Funding Information

Research Protocol

- 1 * Do you have a research protocol to upload?
No, I do not have a research protocol and will use the CICERO application to enter my study information

- 2 If Yes, upload the research protocol:

Name	Created	Modified Date
------	---------	---------------

There are no items to display

ID: VIEW4E00563F8D000
Name: v2_Research Protocol

Risk Level

What is the risk level of your study? (Ultimately, the IRB will determine the appropriate risk level and your designation is subject to change.)

* Choose One:

Greater Than Minimal - Does not meet the definition of Minimal Risk.

ID: VIEW4E02805225800
Name: v2_Risk Level

Type of Research

- 1 * Indicate **ALL** of the types of research procedures involved in this study (Choose all that apply):
Use of unapproved drug(s)/biologic(s) or approved drug(s)/biologic(s) whose use is specified in the protocol.
Psychological/Behavioral/Educational Method or Procedure (i.e., survey, questionnaires, interviews, focus groups, educational tests).
Sample (Specimen) Collection and/or Analysis (including genetic analysis).
Data Collection or Record Review (i.e., chart review, datasets, secondary data analysis).
- 2 * Is this study a clinical trial OR will this study be registered at ClinicalTrials.gov?
A clinical trial is a research study in which one or more human subjects are prospectively assigned to one or more interventions (which may include placebo or other control) to evaluate the effects of those interventions on health-related biomedical or behavioral outcomes.
- Yes No

ID: VIEW4E0280569E000
Name: v2_Type of Research

Lay Summary

- 1 * Provide a summary of the background and purpose of the study in language that can be understood by a person without a medical degree.
This research is being done to help determine the best skin prep for shoulder surgery. Chlorhexidine is used in the operating room as a sterile prep. Chlorhexidine is the current standard operative and preoperative skin prep for all orthopaedic procedures and all parts of the body. The current data supporting it use is strictly based on hip and knee patients. The most common infection after shoulder surgery is from P. Acnes or the same bug that causes skin acne. It is prevalent in shoulder surgery because the shoulder is so close to the neck and back. Current skin preps, like chlorhexidine, in the operating room don't kill this bacteria. Even if we use the skin prep for a few days leading up to surgery, this skin bacteria may still linger. Our dermatology colleagues have a lot of experience with treating skin acne and they recommend trying benzoyl peroxide for a few days before surgery to help reduce shoulder infections. It is simple and safe to use for the past 40 years for the face, neck and back so I now we will try it for the shoulder. Surgical site infection in the orthopaedic surgery population is a big public health issue. Wound infections result in both longer length of hospital stay and total cost of care. Prevention is the key to decreasing this problem.

ID: VIEW4E02805CF7000
Name: v2_Lay Summary

Justification, Objective, & Research Design

If you uploaded a separate research protocol document in the 'Research Protocol' page, cite the applicable section and page numbers from that document in the answer boxes below.

- 1 * Describe the purpose, specific aims, or objectives of this research. State the hypothesis to be tested:
The purpose is to improve skin prep to decrease Propionobacterium Acnes and decrease the rate of shoulder surgical site infection.

Aim 1: To contrast P. Acnes burden after a 3 day prep of chlorhexidine with a 3 day prep of 5% topical benzoyl peroxide.

Aim 2: To estimate decrease in P. Acnes burden with preop skin preps compared to the contralateral side.

We hypothesize that three day preoperative application of 5% topical benzoyl peroxide will decrease patient's P. Acnes bacterial burden in comparison to chlorhexidine (positive control) and in comparison to the nonoperative shoulder (negative control).

- 2

* Discuss the research design including but not limited to such issues as: probability of group assignment, potential for subject to be randomized to placebo group, use of control subjects, etc.:

After surgical posting, patients will be randomized to chlorhexidine or benzoyl peroxide group. The solutions used will be 5% benzoyl peroxide emollient foam and 4% chlorhexidine gluconate skin cleanser. Participants will be instructed to conduct skin wash using the appropriate solution in the shower over the operative shoulder and axilla for three mornings prior to surgery (pre op day -2, pre op day -1, and morning of surgery). Specific instructions will include leaving the solution on the skin for three minutes and avoiding contact with eyes, ears, and mouth. Proper technique will be demonstrated at time of patient recruitment and given as a handout with the wash solution provided. A reminder phone call will occur two days before surgery to remind patients of proper procedure to improve compliance. On the day of surgery, patients be interviewed about pre-operative compliance.

On the day of surgery, two cultures will be taken in three separate sites on both shoulders (anterior, lateral, and posterior) using a detergent scrub technique, the current dermatologic standard for biopsy of the deep sebaceous glands. (3,11) This procedure is typically performed on the skin of awake patients and causes minimal pain and skin irritation. Cultures will be evaluated in our lab. We will also test for hemolysis as a possible indicator of a more virulent strain in the literature.

The research team may take photos of the shoulder skin being swabbed. Photos will not include the facial or defining characteristics. Photos may be taken either in the clinic at time of recruitment or in the operating room when samples are being taken.

Inclusion criteria: all patients undergoing open shoulder surgery or shoulder arthroscopy. Exclusion criteria: anyone with a history of allergic reaction to chlorhexidine or benzoyl peroxide. Anyone with a history of previous shoulder infection, current open skin lesions around the shoulder or the use of current anti-acne medications around the shoulder.

Healthy volunteer portion: Healthy volunteers will respond to the study from fliers on campus. A cotton swab test on both shoulders will be performed prior to any treatment. If a threshold of P. Acnes is met (>1000 CFUs) then volunteers will be randomized to the same two groups and retested after three days of unilateral treatment. Finally, volunteers will undergo repeat cotton swab testing one week after 3 day wash was finalized.

3 * Describe the relevant prior experience and gaps in current knowledge. Describe any relevant preliminary data:

We have no preliminary data at this institution. Current P. Acnes shoulder burden is estimated to be 36% based on recent literature with a periprosthetic infection rate is at least 1-2% with this number expected to increase as more shoulder surgery is expected with the aging population. Economic impact after a shoulder surgical infection is tremendous with additional estimated hospital costs of over \$17,000 per infection not including the impact from wages lost (12).

4 * Provide the scientific or scholarly background, rationale, and significance of the research and how it will add to existing knowledge:

P.acnes is a gram-positive anaerobic bacillus that resides nonpathogenically in the sebaceous glands associated with hair follicles. P.acnes frequently becomes a pathogenic causing infection after arthroscopic and open shoulder procedures. Untreated infections of this nature present with shoulder pain, glenohumeral arthrosis, and arthroplasty failure months or years after a procedure(1). P.acnes forms a biofilm on implant surfaces; cultures taken at the time of surgical revision of failed shoulder arthroplasties are commonly positive for the bacteria(2).

The epidermal skin surface and dermal sebaceous glands are thought to be the source of P.acnes, harboring as many as 105 organisms per follicle(3). P.acnes from these sites are not completely eliminated by standard presurgical skin surface preparations, most likely because bacteria in the dermis cannot be reached by topical surgical preparations (2,3). Surgical incisions transect these area allowing P.acnes to enter the surgical wounds(3) Additionally, preoperative intravenous antimicrobial prophylaxis with traditional skin preparation has not been shown to successfully eliminate P.acnes from the surgical field(2). Thus, while there is evidence to explain the pathogenesis of P.acnes infections in this patient population, there are no effective ways to prevent related post-operative complications.

Conversely, P.acnes that cause facial and truncal inflammatory acne vulgaris have been successfully reduced using short contact benzoyl peroxide (BPO) solutions (4,5,6). BPO is an effective alternative to antibiotics against which P.acnes become more resistant(6). 5.3% BPO emollient foam significantly reduced P.acnes counts on the back by 1.9 log in one week and 2.1 log in two weeks with reduced baseline after discontinued use(7). 5% BPO solutions are maximally effective without negative side effects such as irritation and clothing bleaching observed with higher concentrations(4). Because BPO enhances follicular penetration, it is clinically effective at reducing counts in both the epidermis and dermis(5). Furthermore, BPO has been shown to have potentially beneficial effects on wound healing(8,9,10). 5% BPO washes used before shoulder arthroscopy or open shoulder procedures pose a potential method of reducing P.acnes and minimizing risk of delayed complications from periprosthetic infection.

ID: VIEW4E02805EA0C00
Name: v2_Justification, Objective, & Research Design

Supporting Literature

1 * Provide a summary of current literature related to the research: **If you uploaded a separate research protocol document in the 'Research Protocol' page, cite the applicable section and page numbers from that document in the answer box below.**

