Patients will receive standard of care for all diagnostic or treatment purposes. They will be indicated for shoulder surgery as is the usual protocol. All procedures in the operating room will be under usual protocol including skin prep, sterile procedure as well as a usual post operative protocol and follow up. Patients will be followed to document infection, as would be standard of care as well. Monitoring will be at 2 weeks, 6 weeks, 3 and 6 months as well as 12 months which are standard visits after shoulder surgery and based on the standard protocol of asking the patient about their symptoms. No additional testing will be performed. Patient demographics will be reviewed from the chart.
- * Describe the duration of an individual participant's participation in the study:**

Patients will be monitored for the standard signs of infection for one year after shoulder surgery.

Healthy Volunteers will participate for about 12 days.
- * Describe the amount of time it will take to complete the entire study:**

24 months total. 6 month enrollment period. 12 month follow up. 6 month data analysis and manuscript preparation.
- * Describe any additional participant requirements:**

N/A

ID: VIEW4E0280585B400
Name: v2_Study Procedures

Sample Size and Data Analysis

If you uploaded a separate research protocol document in the 'Research Protocol' page, cite the applicable section and page numbers from that document in the answer boxes below.

- 1 * Provide the rationale and sample size calculations for the proposed target population:
Power analysis. In primary shoulder surgeries, the overall incidence of P. Acnes is 36% in a recent series. We expect a 2/3 decrease in intraoperative incidence. Ninety eight patients are necessary, a 20% attrition rate is expected so a goal of 160 people to be recruited total and about 1/4 to be healthy volunteers.

See below from Stata/SE 13.0 for Mac (64-bit Intel), Revision 17 Jun 2013

```
power twoproportions 0.36 0.12, test(chi2)
Performing iteration ...
Estimated sample sizes for a two-sample proportions test
Pearson's chi-squared test
Ho: p2 = p1 versus Ha: p2 != p1
```

Study parameters:

```
alpha = 0.0500
power = 0.8000
delta = -0.2400 (difference)
p1 = 0.3600
p2 = 0.1200
```

```
Estimated sample sizes: N = 98
N per group = 49
```

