- 2 * Provide the plan for data analysis. Include in the description the types of comparisons that are planned (e.g., comparison of means, comparison of proportions, regressions, analysis of variance, etc.), which is the primary comparison/analysis, and how the analyses proposed will relate to the primary purposes of the study:

Patient will be asked how many times they actually used the skin prep. We will utilize both intention-to-treat and as-treated analyses. We will employ a linear regression based on level of compliance (1 day, 2 day etc.). Paired t-test will be used as a comparison of mean CFUs to the contralateral side (negative control) and the primary outcome will be based on an aggregate chi-square comparison of proportions between chlorohexidine and benzoyl peroxide groups.

ID: VIEW4E02806052800
Name: v2_Sample Size and Data Analysis

Sharing of Results

- 1 * Describe whether results (study results or individual subject results, such as results of investigational diagnostic tests, genetic tests, or incidental findings) will be shared with subjects or others (e.g., the subject's primary care physicians) and if so, describe how it will be shared:

The results of specific tests and the overall study will not be shared with participants. The results will not affect the standard of care for each patient.

ID: VIEW4E02808CBD800
Name: v2_Sharing of Results

Research with Drugs or Biologics

You indicated on the "Type of Research" page that your study involves use of unapproved drug(s)/biologic(s) or approved drug(s)/biologic(s) whose use is specified in the protocol AND/OR evaluation of food(s) or dietary supplement(s) to diagnose, cure, treat, or mitigate a disease or condition.

- 1 * List all drugs/biologics to be administered in this study. Be sure to list each drug/biologic with its generic name only.

Drug Name	FDA Approved	IND Number	PI IND Holder
View Benzoyl Peroxide	yes		no
View Chlorhexidine	yes		no

- 2 * Attach the drug package insert or investigational drug brochure for the drugs being administered in this study:

5% BPO Label.jpg	8/26/2015 10:51 AM	8/26/2015 10:51 AM
Chlorhex 4%.png	3/30/2015 9:48 PM	6/17/2015 10:30 AM

- 3 If more than one drug is administered, discuss the risk implications of drug/therapy interactions:
Drugs will not be administered simultaneously

- 4 * Will you be using Investigational Drug Services?

Yes No

ID: VIEW4E0916E6E1400
Name: v2_Research with Drugs or Biologics

Drug or Biologic Storage and Handling

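### The reminder call is set for the day of the first morning wash, with no clock time, so it is not assured to come before the first of the three washes

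*Combined protocol and SAP*

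**What the plan says.** The relevant text is in the combined protocol and SAP, under Justification, Objective, & Research Design, item 2. Surgical patients wash the operative shoulder and axilla in the shower "for three mornings prior to surgery (pre op day -2, pre op day -1, and morning of surgery"). In the same paragraph: "A reminder phone call will occur two days before surgery to remind patients of proper procedure to improve compliance". The call has no time of day, and no other reminder is described.

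The paragraph also provides earlier instruction: "Proper technique will be demonstrated at time of patient recruitment and given as a handout with the wash solution provided". Additional Documents lists a separate instruction file for each product; the contents are not shown.

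Adherence enters the analysis by self-report. Sample Size and Data Analysis, item 2, says "Patient will be asked how many times they actually used the skin prep". It plans intention-to-treat and as-treated analyses, and adds: "We will employ a linear regression based on level of compliance (1 day, 2 day etc"). Aim 1 is defined by the full course: "To contrast P. Acnes burden after a 3 day prep of chlorhexidine with a 3 day prep of 5% topical benzoyl peroxide".

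The healthy volunteer portion describes no reminder call, so the point concerns surgical patients only.

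**The concern.** The call exists to improve compliance with a procedure that has specific steps, including a three-minute contact time. A reminder serves that purpose best when it comes before the first use. Here it falls on the day of first use, and that use is in the morning. If staff call during the working day, after the patient has showered, the call can neither prompt the first wash nor correct how it was done.

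The first wash is one of three, so a third of the planned applications lies outside the sure reach of the call. A missed first wash reduces the exposure that Aim 1 compares and, if washes add to the effect, dilutes the intention-to-treat contrast. It also produces more of the partial compliance that the as-treated analysis and the compliance regression must handle. Those analyses compare patients by self-reported use, which is not randomised.

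**Working it through.** **Step 1: the dates.** Count the day of surgery as day 0.

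- Washes: mornings of day -2, day -1 and day 0 (design section, item 2).
- Call: two days before surgery, which is day -2 (same paragraph).
- Lead time from call to first wash: (-2) - (-2) = 0 days.

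With no clock time, a call on day -2 may come before or after the morning wash. If it comes before, it can support 3 of 3 washes. If after, it can support 2 of 3 (67%).

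**Step 2: the plan's own sample size.** Sample Size and Data Analysis, item 1, gives the Stata command "power twoproportions 0.36 0.12, test(chi2"), with alpha 0.05 two-sided, power 0.80, and 49 per group (98 in total). With p1 = 0.36, p2 = 0.12 and mean p = 0.24:

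n per group = [1.960 × √(2 × 0.24 × 0.76) + 0.842 × √(0.36 × 0.64 + 0.12 × 0.88)]² / 0.24²

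= [1.960 × 0.6040 + 0.842 × 0.5797]² / 0.0576 = 48.5, rounded up to 49.

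The stated figure reproduces. Power at 49 per group is 80.4%.

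**Step 3: an illustration of size.** The documents give no call time, no expected rate of missed washes and no estimate of what a reminder achieves. The following assumptions are therefore mine:

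- the fall from 36% to 12% is linear in washes, so each wash contributes (36 - 12)/3 = 8 percentage points;
- chlorhexidine stays at 36%;
- there are 49 patients per arm;
- f is the share of the benzoyl peroxide arm who miss the first wash *because of* the call's timing, that is, the extra misses that an earlier call would have prevented.

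The benzoyl peroxide rate is then p2 = 0.12 + 0.08f, and

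power = Φ{[(0.36 - p2) - 1.960 × √(2p̄(1 - p̄)/49)] / √[(0.36 × 0.64 + p2(1 - p2))/49]}, where p̄ = (0.36 + p2)/2.

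| f | p2 | Power |
|---|---|---|
| 0 | 12.0% | 80.4% |
| 2% | 12.16% | 79.8% |
| 5% | 12.4% | 78.8% |
| 10% | 12.8% | 77.1% |

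For f = 10%: p̄ = 0.244, the two standard errors are 0.0868 and 0.0835, and (0.232 - 1.960 × 0.0868)/0.0835 = 0.74, which gives 77.1%.

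**The case against.** The strongest reply is that a late call is not a missed wash. Patients are shown the technique at recruitment and keep a handout supplied with the solution. Even in the worst case the call still supports the washes on day -1 and the morning of surgery. The call and instructions are described for both groups alike, so the timing does not favour one arm. Any dilution would move the intention-to-treat result towards no difference and would not create a false positive. Compliance is asked about on the day of surgery and is used in the analysis. The expected two-thirds decrease is not said to assume perfect adherence, so some missed washes may already be inside the 12%. All of this stands, and it keeps the point small. It does not remove the overlap of dates: a handout is not a timed prompt, and the plan itself chose to add one.

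Three stronger readings are tempting, and the documents do not support them.

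- *The call comes too late for many patients.* No call time is stated, so the share cannot be known. The text supports only that the call is not assured to come first.
- *The call exists because instruction was given weeks earlier.* No interval from recruitment to surgery is stated. The only purpose given for the call is to remind patients of procedure and improve compliance.
- *Power could fall to about 62%.* On the linear model above, that needs f = 50% (p2 = 16%). Half the benzoyl peroxide arm would have to miss the first wash solely because of when the call was made. Misses that would occur whatever the call date do not count against its timing.

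**Conclusion.** The point holds as a minor, low-cost adherence improvement for surgical patients. The same-day overlap is plain from the two dates and is not resolved elsewhere in the documents. It leaves the first of three washes without an assured reminder. The number of patients affected cannot be computed. If the extra misses run from 2% to 10% of the benzoyl peroxide arm, the loss is between about half a percentage point and about three points of power. That range rests on the assumed linear effect per wash, an unchanged chlorhexidine rate and 49 patients per arm; it is an illustration, not a forecast. The sample size of 98, the endpoint and the planned analyses are not called into question by this point.

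**What to change.** In the design section, item 2, schedule the existing reminder call so that it comes before the first wash, for example on the day before pre-op day -2. The products, the wash days and the compliance interview stay as written. The only cost is changing the call date, since the call is already planned.

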1 * What type of samples will be involved in this study? (Check all that apply)

Prospective (will be collected)

2 * Will genetic analysis/testing be done on any of the samples?

Yes No

- 3 * Will this study involve banking of samples (storing for future research use)?
 Yes No
- 4 * What is the purpose of the sample collection and/or analysis?
 To identify P. Acnes burden
- 5 * Is there the possibility that cell lines will be developed with any of the samples?
 Yes No
- 6 * Will the samples be released to anyone not listed as an investigator on the protocol?
 Yes No
- 6.1 If Yes, give name(s) and affiliation(s):
- 7 * Will the sample material be sold or given to any third parties?
 Yes No
- 7.1 If Yes, give name(s) and address(es):

ID: VIEW4E0E1A4B80000
 Name: v2_Sample Collection/Analysis

Prospective Samples

You indicated that the study involves collection of prospective samples (specimens).

- 1 * What type of sample will be collected? (Check all that apply)
 Other
- 1.1 If Other, specify:
 Skin follicles sampling from a skin swab
- 2 For blood draws, specify the amount drawn, in teaspoons, at each visit and across the course of the subject's entire participation time:
- 3 * What type of samples will be collected? (Check all that apply)
 Samples obtained specifically for research purposes-obtained via a separate collection procedure done solely for the purposes of the study
- 3.1 If Other, specify:
- 4 * How are these samples labeled? For example, do they contain name, initials, dates, Social Security number, medical record number, or other unique code?
 Labeled with unique patient identifier established at time of enrollment
- 5 * Will sample(s) be made available to the research subject (or his/her medical doctor) for other testing?
 Yes No
- 6 * If a participant withdraws from the study, will that participant have the option to get the remaining portion of their sample(s) back?
 Yes No
- 7 * If the participant withdraws, explain how their sample(s) will be handled (For example, will sample(s) be destroyed, anonymized, etc.):
 Samples will be destroyed.
- 8 * Will the samples be destroyed after the study is over?
 Yes No
- 8.1 If No, describe how the samples will be stored, where they will be stored, and for how long.

ID: VIEW4E0E257D60C00
 Name: v2_Prospective Samples

Data Collection/Record Review

You indicated on the "Type of Research" page that your study involves data collection or record review (i.e., chart review, not self-report).

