- * Where will research data be kept (address electronic and paper data as applicable)? (If this is a VA study please list specific sites that data will be kept.)**
All study records will be identified by coded number to maintain patient confidentiality. All electronic records will be identified by coded participant numbers, and will be password protected. Clinical information will not be released without written permission from the patient, except as needed for monitoring by the IRB. Data will be in stored in a locked office in the Allied Health Building at the University of Maryland Medical Center. Only the study team will have access to this information.

- 3 * How will such data be secured?
All data will be password protected and/or locked in an office to which there is limited access. Data will be stored in a locked office in the Allied Health Building at the University of Maryland Medical Center. Only the study team will have access to this information.
- 4 * Who will have access to research data?
Identifiable data will be accessible to the investigator and study team at the site.
- 5 * Will study data or test results be recorded in the participant's medical records?
 Yes No
- 6 * Will any data be destroyed? **(Please note that data for FDA regulated research and VA research cannot be deleted)**
 Yes No
- 6.1 If Yes, what data (e.g., all data, some recordings, interview notes), when and how?
Study records will be maintained in accordance with current ICH guidelines. Data will be maintained for five years following the end of research-related activities. At the end of this period, each site will provide the Coordinating Center a signed verification that these data have been destroyed.
- 7 Do you plan to obtain a Certificate of Confidentiality?
 Yes No
- 7.1 If Yes, upload your Certificate of Confidentiality. If you have not yet obtained the Certificate, please note that once it is obtained, you will need to submit an amendment to attach the document, make any needed changes to the submission and make needed changes to the Informed Consent Document.
- | Name | Created | Modified Date |
|-------------------------------|---------|---------------|
| There are no items to display | | |
- 8 * Discuss any other potential confidentiality issues related to this study:
N/A

ID: VIEW4E1B5265E0400
Name: v2_Confidentiality of Data

Monitoring Plan Selection

- 1 * Type of data safety monitoring plan for the study:
Data Safety Monitoring by an Individual

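### The plan describes no step that keeps culture readers unaware of arm or treated shoulder; random specimen codes in place of the enrolment identifier would close that gap cheaply.

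*Combined protocol and SAP*

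**What the plan says.** All references are to the combined protocol and SAP.

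- **Interventions** (Justification, Objective, & Research Design, item 2): "The solutions used will be 5% benzoyl peroxide emollient foam and 4% chlorhexidine gluconate skin cleanser". The same item adds: "Proper technique will be demonstrated at time of patient recruitment and given as a handout with the wash solution provided". The Additional Documents page lists a separate instruction sheet for each product.
- **Day of surgery** (same item): "On the day of surgery, patients be interviewed about pre-operative compliance". On that day "two cultures will be taken in three separate sites on both shoulders (anterior, lateral, and posterior) using a detergent scrub technique", which is 2 × 3 × 2 = 12 cultures per patient.
- **Reading** (same item): "Cultures will be evaluated in our lab". Hemolysis is also to be tested. The reader is not identified, and no positivity rule is given for surgical patients. The threshold of more than 1000 CFUs applies only to whether healthy volunteers are randomized.
- **Labelling** (Prospective Samples, item 4): "Labeled with unique patient identifier established at time of enrollment". No separate laboratory code is described.
- **Access** (Confidentiality of Data, item 4): "Identifiable data will be accessible to the investigator and study team at the site".
- **Analysis** (Sample Size and Data Analysis, item 2): "the primary outcome will be based on an aggregate chi-square comparison of proportions between chlorohexidine and benzoyl peroxide groups". A paired t-test compares mean CFUs with the contralateral shoulder.
- **Hypothesis** (Justification, Objective, & Research Design, item 1): benzoyl peroxide is expected to give a lower burden than chlorhexidine and than the nonoperative shoulder.

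The text available for review says nothing about masking of participants, sample collectors, culture readers or analysts. The Research Protocol page states that no separate protocol exists.

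**The concern.** Both comparisons rest on how plates are read: growth or no growth for the proportions, and colony counts for the paired test. I assume, as a matter of general experience and not from the documents, that calling growth, counting colonies and grading hemolysis leave some room for judgement. The missing positivity rule widens that room.

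The team expects a particular direction. If a reader knows the arm, borderline calls can lean that way and create a between-arm difference that is not real. If a reader knows which shoulder was washed, the same can happen in the Aim 2 comparison. Neither can be corrected once unmasked readings have been recorded. Masked misreading is less harmful: it affects both arms alike, so it costs power but does not create a difference where none exists.

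**Working it through.** **1. Can a reader reach the allocation?** Participant Selection, item 2 defines enrolment as signing consent, and Study Procedures, item 1 places randomization after consent. An identifier set at enrolment therefore cannot encode the arm. It does identify the patient to anyone who can link it, and Confidentiality of Data, item 4 gives the study team access to identifiable data. Team members who demonstrate a wash and hand it over know the arm. No passage keeps plate readers outside that group or gives specimens a second code. The exposure is possible and nothing described prevents it; it is not shown to occur.

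**2. The plan's own sample size.** Inputs from Sample Size and Data Analysis, item 1: p1 = 0.36, p2 = 0.12, two-sided alpha 0.05, power 0.80, Pearson chi-square. The mean proportion is p̄ = 0.24.

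n per group = [1.960·√(2·p̄·(1−p̄)) + 0.8416·√(p1(1−p1) + p2(1−p2))]² / (p1−p2)²
= [1.960·√0.3648 + 0.8416·√0.3360]² / 0.0576
= [1.184 + 0.488]² / 0.0576 ≈ 48.5, rounded up to 49.

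The total is 98, as the plan states, with power of 80.4% at 49 per group. This point does not dispute that figure.

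**3. False-positive rate under differential reading.** Assume no true difference, with 24% positive in each arm (the midpoint of 36% and 12%) and 49 per arm. Let p1 and p2 now be the proportions *as read* for chlorhexidine and benzoyl peroxide, and d = p1 − p2.

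s0 = √(2·p̄·(1−p̄)/49), s1 = √((p1(1−p1) + p2(1−p2))/49)

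P(reject) = Φ((d − 1.960·s0)/s1) + Φ((−d − 1.960·s0)/s1)

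For 0.29 against 0.19: s0 = 0.0863 and s1 = 0.0857. The terms are Φ(−0.807) + Φ(−3.14) = 0.210 + 0.001 = 0.211.

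The table gives exact binomial enumeration; the formula agrees within about 0.1 percentage point.

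| As read: chlorhexidine / benzoyl peroxide | Net gap (points) | False-positive rate |
|---|---|---|
| 24% / 24% | 0 | 5.0% |
| 26% / 22% | 4 | 7.5% |
| 27% / 21% | 6 | 10.6% |
| 29% / 19% | 10 | 21.2% |
| 24% / 22% | 2 (one arm) | 5.7% |
| 24% / 21% | 3 (one arm) | 6.5% |
| 24% / 19% | 5 (one arm) | 9.3% |

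The 10-point gap is a demanding assumption. It needs 5/24 = 21% of benzoyl peroxide positives to be missed and 5/76 = 7% of chlorhexidine negatives to be called positive.

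**4. A second illustration.** Suppose true positivity is 36% in both arms and a share of benzoyl peroxide positives is read as negative. By the formula, shares of 10%, 20% and 30% give 6.6%, 11.8% and 21.1%. At 24% positivity the same shares give 5.9%, 8.9% and 14.2%.

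**5. Masked reading for contrast.** If 10% of positives are missed in both arms, the false-positive rate stays at 5%, and power at 36% against 12% falls from 80.4% to 74.6%. If 20% are missed, power falls to 68.0%.

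**The case against.** The strongest reply is that the plan is silent, and silence is not a statement that readers are unmasked. The document does not say who reads the plates or whether they see study forms, and it never uses the term open-label. Visibly different products justify that term for patients and for staff who hand out the wash, not automatically for a laboratory reader. Likewise, the compliance interview shows that some staff may learn the arm on the sampling day; it does not show that the reader does. All of this stands, and it is why the point is worded as a missing safeguard.

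A reader might infer that the specimen label reveals the allocation, or that it is the same code as in the allocation record. The documents do not support either. The identifier is set before randomization, and no allocation record or its coding is described. Privacy of Participants, item 1 says study forms carry a coded number, but not that this number is the specimen label. That section also restricts the log matching codes to names to local clinic staff. This weakens the route to linkage but does not close it, because Confidentiality of Data, item 4 gives the wider study team access to identifiable data.

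The shoulder needs the same care. No side marking on specimens is described, and a left or right mark alone would not tell a reader which shoulder was washed. Knowing the shoulder mainly bears on Aim 2, not on the between-arm primary test.

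Finally, cultures are laboratory measures and the true misreading rate may be small. If one arm shifts by only 2 or 3 points, the false-positive rate barely moves.

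**Conclusion.** The point holds as a gap in the plan. Specimens carry a patient-level identifier, they are read in the study's own lab, the team can reach identifiable data, and no step keeps readers unaware of arm or treated shoulder. The primary and Aim 2 comparisons are open to differential reading.

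The size is unknown. Within the assumed range at 24% positivity and 49 per arm, the false-positive rate runs from about 5.7% (one arm shifted by 2 points) to about 21% (a net gap of 10 points). Every shift is an assumption, and so is the view that plate reading involves judgement. A reader might infer that the primary outcome is already shown to be biased; the documents do not show that. The case for acting rests on the low cost of the safeguard and on the fact that biased readings cannot be repaired afterwards.

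**What to change.** In Prospective Samples, item 4, replace the enrolment identifier on specimens with a random code for each specimen that shows neither patient, arm nor side. The key should record patient, shoulder, site and replicate, and be held by an existing team member who does not read plates. Link codes to patients only after culture results and CFU counts are locked. State in Justification, Objective, & Research Design, item 2 that readers are masked to arm and treated shoulder. If masking is already practised, describe it there.

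**Cost.** A second code list, at 12 codes per surgical patient (98 × 12 = 1,176 for the 98 patients required), and a small risk of linkage error, which a check of the key against the specimen log would limit. Through the key, samples can still be located for destruction if a participant withdraws (Prospective Samples, item 7). The sample size stays at 98 and no patient procedure changes.

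**Limit.** This removes reading bias only. It does not remove bias from an unmasked person performing the scrub, or differences in compliance between the arms.
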